MOBILE Intervention in College Students with Elevated Blood Pressure

Version Date: 05/19/2021

Protocol and Procedures

Protocol and Procedures

Aim 1 Formative research design. We will recruit two student panels (4-5 students each) to further refine the **MOBILE** intervention and assist in developing measures used in the study. We will recruit one set of student panel at a time. This 4-month phase will enable the team to design an extensive list of SMS messages tailored to different levels of motivation. In a 4-week intervention, enough messages are needed to ensure no message will be sent more than twice. Given 3 levels of motivation (1-low, 2-moderate, and 3-high), each level requiring different prompting messages, at least 42 (28 days x 3 levels = 84/2 = 42) messages need to be created across the 3 levels. The team will draft an initial set of messages, drawing content from the American Heart Association high BP recommendations;⁶⁰ each message's behavioral suggestions will correspond to each of the 3 motivation levels. Students will be surveyed to rank the effectiveness of each message; they will be asked to assess how clear, compelling, engaging, and motivating each message is in itself and how effective each message might be in propelling them to action. The investigative team will identify strong and weak messages, characterizing what makes strong messages strong. The team will then build a revised list of messages, discarding the weakest, or use what we have learned to strengthen the weaker messages. We will repeat this process with the second group of students using the revised list of messages and use those results to build a stronger final set of messages to be used in the implementation phase of the study. This iterative approach will also refine the study's motivational scale and self-report survey. This phase will be held via zoom with no in-person contact.

Aim 2 and Exploratory Aim Research Design. The proposed pilot study will use a randomized two-arm intervention and control group design to test the preliminary impact of the **MOBILE** intervention. The PI will be involved in all aspects of study and will train a research assistant (RA) to provide the educational session, monitor subjects, and address technology challenges.

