Baseline data collection. Baseline data collection (using Qualitrics) will occur before the start of the educational session, described below. Subjects with blood pressure value less than 120/80 mm Hg during this visit (second blood pressure reading) will no longer qualify for this study. The gold standard BP measurement using a sphygmomanometer through auscultation will be taken twice, five minutes apart to be averaged. Other baseline data include: anthropometry (height and weight), Automated Self-Administered 24-Hour Dietary Assessment Tool (ASA24) focusing on sodium intake, pre-test Hypertension Knowledge-Level Scale (HK-LS), and initial motivational level assess (using Qualitrics) using the study's iPads. We have two research iPads that are only designated for this project. The subjects will not use their own devices and the link are not send to subjects. It is already set up to collect data from the subjects. We locked the screen on the iPads so only the questionnaires can be accessed.

Aim 2 Educational session, all subjects. The PI or RA will provide a brief one-on-one or group educational talk (no more than 2 subjects, to separate intervention and control group subjects) before the 4-week trial on the importance of SMBP, elevated BP regarding CVD risk, the role of motivation in adopting lifestyle behavior, and specific behaviors to reduce BP. This is akin to HTN risk reduction advice received in an office visit.

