Aim 2 MOBILE Intervention Group. Following the educational session, intervention subjects will receive a Withings BP cuff and Health Mate app will be installed on their smartphone. *The research team will create a username (subject's ID for the study to maintain confidentiality) for each subject.* By consenting, subjects will grant us access to their recordings and direct access to app manufacturer data on them. As a second layer, we will also ask the subjects to send the research team their daily blood pressure value to ensure we have the data and continual daily communication. We will show them how to use the Health Mate app, upload Withings BP cuff readings, upload historical data to the cloud, read trend lines in their record, rank their daily motivational level, and answer a brief SMS question about whether they completed the behavioral change task encouraged by the daily message. A one-page instruction sheet with the research team's contact information will be provided. In addition to addressing questions, the session will offer the opportunity to practice using and entering data on the app. Subjects' use of the app will be assessed and followed-up within 72 hours by the RA to ensure subjects' comfort level using the instruments and app. Subjects will be instructed to take their BP daily, before their first meal and encouraged to avoid prior alcohol and caffeine intake as well as physical activity. They will be instructed to rate their motivational level as low, moderate, or high via SMS when transmitting their BP value. Their level will trigger the appropriate behavioral change SMS prompt. Thus, a subject at a high motivational level – because they feel good about having their BP in the normal range – will receive an encouraging text message ("keep up the good work") along with a prompt to complete a difficult task (e.g. do some form of physical activity for 30 minutes). On a low motivation day, a subject might be encouraged to look up low-salt salad dressing recipes online. Subjects will receive a reminder SMS if they have not provided their daily BP. *This is not a physical activity or dietary intervention; therefore, specifically physical activity or dietary education will not be provided, rather this is a behavioral intervention that encourages the subjects to engage in healthy behaviors that they have previous experience to draw from, with additional information provided during the educational session, to reduce their blood pressure value.*

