If we haven't heard from the subject for more than 7 days, we will invite the subject to a meeting to explore why the subject hasn't been participating. Such meetings will give us an opportunity to identify barriers and challenges subjects are experiencing and to remind them why they enrolled in the first place. An RA will contact each subject two times during the 4-week intervention to (a)

explore the acceptability of and engagement with the intervention and (b) reinforce study participation. Subjects can always withdraw from the study if they wish to do so.

Aim 2 Control Group. Following the educational session, the control group subjects' BP, ASA24 (sodium intake), and pre-test knowledge on HTN will be obtained (using Qualtrics). Four weeks later, the subject will be scheduled for a follow-up meeting to collect each subject's BP, ASA24, and post-test knowledge on HTN (using Qualtrics).

Aim 2 Post-intervention data collection and intervention engagement. We will schedule a post-intervention meeting with each subject for data collection (gold standard BP) and return of the Withings BP cuff (intervention group only). We operationalize acceptability, the key Aim 2 outcome, as the subject's favorable perception of the **MOBILE** intervention as being appropriate and reasonable in addressing their elevated BP, convenient to use, easy to apply to their daily lives, and effective in addressing their elevated BP both currently and long-term. Data on acceptability and other study variables will be gathered using questionnaires and open-ended questions in a semi-structured exit interview (using Qualtrics). The research team will monitor the intervention for subject acceptability operationalized as active and continual participation in the intervention (receiving the subject's daily BP value), and favorable responses to the tailored change behavior SMS. The team will also measure engagement with the intervention, operationalized as the extent to which the subject followed the self-monitoring protocol. The self-report survey and semi-structured interview script will be created and implemented by the research team during the formative phase. The intervention subjects will be informed that they may delete the Health Mate app at any time once their participation is completed. The research team will no longer have access to their BP data once they completed the study.

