Data Analysis. Aim 2: We will perform preliminary descriptive analyses on all variables, use Pearson's correlation (r) to assess relationships between primary and secondary outcome variables at each data collection point, and calculate Pearson's r to assess the stability of each outcome variable pre- and post-intervention. To evaluate feasibility and acceptability, we will use content analytic methods to identify students' likes and dislikes and suggestions for future app improvement.⁶⁵ Thematic analysis of interviews will be conducted to describe the elements of feasibility and acceptability as perceived by subjects. Participation rate will be calculated as the percentage of students enrolled out of all eligible students who are invited to participate in the study; engagement will be calculated as a percentage of students' available data out of all the intended data points. **Exploratory Aim.** "The intervention group will have a significantly greater reduction in BP and sodium intake and greater increase in HTN knowledge from baseline to completion, compared to control group." A 2x2x2 mixed design ANCOVA will be performed for each of the above primary and secondary outcomes, with Study Group (Intervention vs. Control) as the between-subject factors, years of age as the covariate. A Time effect on an outcome variable would indicate the impact of the **MOBILE** intervention on the outcome measure in college students with elevated BP.

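### The plan does not say who takes the auscultatory BP or keep that reader unaware of arm and earlier values, so observer expectation can enter the exploratory between-arm BP comparison

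*Protocol*

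**What the plan says.** **Method.** The Protocol (Baseline data collection) defines the measurement: "The gold standard BP measurement using a sphygmomanometer through auscultation will be taken twice, five minutes apart to be averaged". The post-intervention paragraph reuses the gold-standard label without redefining it, so auscultation carries over to follow-up.

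**Follow-up visit.** "We will schedule a post-intervention meeting with each subject for data collection (gold standard BP) and return of the Withings BP cuff (intervention group only". The questionnaires and the exit interview also belong to post-intervention data collection. No order is given and no reader is named.

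**Staff.** The Protocol (Aim 2 and Exploratory Aim Research Design) says: "The PI will be involved in all aspects of study and will train a research assistant (RA) to provide the educational session, monitor subjects". For the education, "The PI or RA will provide a brief one-on-one or group educational talk". In the MOBILE arm, subjects' "use of the app will be assessed and followed-up within 72 hours by the RA", and an RA makes two further contacts during the four weeks. Investigative and research teams are also mentioned, without a list of members.

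**Data flow.** The Protocol (Aim 2 MOBILE Intervention Group) adds a second route for home readings: "ask the subjects to send the research team their daily blood pressure value". Nothing comparable is described for controls.

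**Baseline timing.** Baseline data collection is placed ahead of the educational session. The Aim 2 Control Group paragraph places the controls' BP after it.

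**Use.** The SAP (Data Analysis) states the Exploratory Aim hypothesis: "The intervention group will have a significantly greater reduction in BP and sodium intake", relative to control.

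**The concern.** An auscultatory reading requires a person to decide when the sounds begin and end and to round to a mark on the scale. Averaging two readings reduces random error but leaves a consistent lean by the observer untouched.

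Three features let knowledge of the arm reach that person. The team follows MOBILE subjects' home BP for four weeks. A cuff handed back at the follow-up meeting reveals the arm if it comes before the BP reading. And no provision separates the reader from the people who run the intervention. If control baseline BP is really taken after education, the same exposure may exist at baseline, because education sessions are arranged to keep the arms apart and the arm is therefore known by then.

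At stake is the between-arm BP change. It is exploratory, but it is the effect on which the sample size was built. The planned ANCOVA cannot tell a reader effect from a treatment effect, and recruiting more subjects, as both documents hope to do, does not shrink a reader effect.

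**Working it through.** The documents give no figure for observer error and no BP SD, so there is no plan figure to reproduce. The check has two parts.

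**1. What protects the reading?**

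- Reader named: no, at either visit.
- Reader unaware of arm: not provided for.
- Earlier clinic or home values concealed: not provided for.
- Order of BP, interview and cuff return: not set.
- Same information held on both arms: no, daily home BP for MOBILE only.
- Control baseline BP before education: the two Protocol paragraphs disagree.

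**2. How large could the effect be?**

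Inputs from the documents: 16 per arm randomised; 28 evaluable in total, so 28 / 2 = 14 per arm; correlation r = .5 between the two measurements; alpha 0.05, taken as two-sided.

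Assumed inputs: a share p of MOBILE follow-up readings is rounded down by one 2 mmHg mark, with no shift in controls; BP SD 8, 10 or 12 mmHg; no true effect.

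Shift in the arm difference = p × 2 mmHg:

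- p = 0.25: 0.25 × 2 = 0.5 mmHg
- p = 0.50: 0.50 × 2 = 1.0 mmHg
- p = 1.00: 1.00 × 2 = 2.0 mmHg

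With two arms and two time points, and leaving out the age covariate, the group-by-time test is a t test on change scores:

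- SD of change = SD × √(2(1 − r)) = SD × √(2 × 0.5) = SD
- Standard error of the arm difference = SD × √(2/n)
- Noncentrality = shift / standard error, with 2n − 2 degrees of freedom

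Example with SD 10, n = 16 per arm and a 2 mmHg shift: standard error = 10 × √(2/16) = 3.54; noncentrality = 2 / 3.54 = 0.57. The observed difference must reach 7.22 mmHg to be significant, and the chance of that in MOBILE's favour is 7.9%.

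Chance of a significant result favouring MOBILE when there is no true effect:

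| Shift (mmHg) | n per arm | SD 8 | SD 10 | SD 12 |
|---|---|---|---|---|
| 0 | 14 or 16 | 2.5% | 2.5% | 2.5% |
| 1 | 14 | 5.0% | 4.4% | 4.0% |
| 1 | 16 | 5.3% | 4.6% | 4.2% |
| 2 | 14 | 9.3% | 7.4% | 6.2% |
| 2 | 16 | 10.1% | 7.9% | 6.6% |

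For a fixed shift the chance rises slightly from 14 to 16 per arm, because a larger sample estimates the biased difference more precisely.

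**The case against.** This is a pilot with acknowledged low power. Its key Aim 2 outcome is acceptability, and auscultation is a deliberate choice of reference method. The shifts above are small, and the largest requires every MOBILE follow-up reading to be rounded down. All of that stands, and it limits the weight of the point.

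Three stronger readings are tempting, but the documents do not support them.

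- A reader might infer that the staff who deliver MOBILE take the endpoint reading. No sentence says so. The PI's broad role and the lack of any separate assessor make it plausible, but the supported statement is that the plan does not identify or mask the reader.
- A reader might infer that the bias must favour MOBILE. That follows only from assuming rounding down. Someone who has seen persistently high home values may expect, and record, a high reading.
- A reader might infer that nothing in the plan could reveal the problem. A MOBILE clinic fall that the home trend does not mirror would be a warning. That check is imperfect, because clinic and home readings differ in setting and device and controls have no home series.

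It can also be said that taking BP first does not blind someone who already knows the arm. That is correct: such a rule removes the cues at the visit, not prior knowledge.

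**Conclusion.** The point holds as a possibility that the plan leaves open. An observer-dependent BP reading, an unnamed and unmasked reader, MOBILE-only daily data and a visit with no set order together allow expectation to enter the exploratory BP comparison. Size and direction are unknown from the documents. Under the assumed one-sided 2 mmHg rounding the shift is at most 2 mmHg, and a false result favouring MOBILE then has a chance of 6.2% to 10.1% instead of 2.5%. At half that shift the range is 4.0% to 5.3%. These percentages rest on the assumed SD of 8 to 12 mmHg and on a change-score test without the age covariate. Acceptability is not affected. The change is worth making because most of it costs only wording.

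**What to change.** 1. In the Baseline data collection and Post-intervention data collection paragraphs, state that at both visits and in both arms BP is taken first, before education, questionnaires, interview and cuff return, with the subject's earlier clinic and home values out of the reader's view.
2. Reconcile the Aim 2 Control Group paragraph with Baseline data collection, so that baseline BP falls at the same point in both arms.
3. Where staffing allows, have follow-up BP in both arms read under one rule by an existing team member who did not handle MOBILE contacts or daily data. The rule must cover controls too; reassigning the reader for MOBILE subjects alone could confound reader with arm. Where this is not possible, report the BP result as unmasked.
4. Optionally, if a study-owned cuff is available (the documents do not confirm one), add parallel automated readings in both arms. Report them as a sensitivity check, noting that MOBILE subjects are more familiar with the device.

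Cost: Protocol wording and minor scheduling constraints, with existing staff. Item 4 would add some visit time and a second BP result to report. Masking stays partial, because staff may already know the arm.

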MOBILE Intervention in College Students with Elevated Blood Pressure

Version Date: 05/19/2021

Statistical Analysis Plan

Statistical Design and Power

Sample size. We will recruit 32 subjects to be randomized to an intervention and control arm with a ratio of 1:1 ($n = 16$ per study group), using a random number generator. A sample size comparable to a prior study of cellular phone and internet-based intervention on BP reduction that showed medium to high effect sizes (ES $f = 0.395$) on BP reduction.⁴⁹ Using an estimated ES of $f = 0.39$ for the within-subject effect (Time), we conducted a power analysis for a mixed design ANCOVA with 2 groups, 2 measurements per subject, and $r = .5$ for the bivariate correlation between two measures tested at $\alpha = 0.05$. To achieve 70% power for the significance test of the within-between interaction effect, a sample of $N = 28$ will be needed. Anticipating a 7-11% attrition rate⁴⁹ based on the previous study,⁴⁹ an initial $N = 32$ will be needed to achieve 70% power to test preliminary impact. We acknowledge that the low power level is a limitation in our pilot study; therefore, we will attempt to recruit more within the timeframe to reach a higher power level.

Data Analysis. Aim 2: We will perform preliminary descriptive analyses on all variables, use Pearson's correlation (r) to assess relationships between primary and secondary outcome variables at each data collection point, and calculate Pearson's r to assess the stability of each outcome variable pre- and post-intervention. To evaluate feasibility and acceptability, we will use content analytic methods to identify students' likes and dislikes and suggestions for future app improvement.⁶⁵ Thematic analysis of interviews will be conducted to describe the elements of feasibility and acceptability as perceived by subjects. Participation rate will be calculated as the percentage of students enrolled out of all eligible students who are invited to participate in the study; engagement will be calculated as a percentage of students' available data out of all the intended data points. **Exploratory Aim.** "The intervention group will have a significantly greater reduction in BP and sodium intake and greater increase in HTN knowledge from baseline to completion, compared to control group." A 2x2x2 mixed design ANCOVA will be performed for each of the above primary and secondary outcomes, with Study Group (Intervention vs. Control) as the between-subject factors, years of age as the covariate. A Time effect on an outcome variable would indicate the impact of the **MOBILE** intervention on the outcome measure in college students with elevated BP.

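### The stated 70% power at N = 28 does not follow from f = 0.39, r = .5 and alpha = .05, and no effect size is given for the interaction being tested

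*SAP*

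**What the plan says.** The SAP (Statistical Design and Power, Sample size) and the Protocol (Aim 2 Sample size) carry the same calculation. The effect size comes from a previous phone and internet intervention reported to show "medium to high effect sizes (ES $f = 0.395$) on BP reduction". The plan continues: "Using an estimated ES of $f = 0.39$ for the within-subject effect (Time), we conducted a power analysis", for a mixed-design ANCOVA with two groups, two measurements per subject, a correlation of .5 between them and alpha of 0.05. The result is: "To achieve 70% power for the significance test of the within-between interaction effect, a sample of $N = 28$ will be needed". An allowance of 7-11% for attrition takes 28 to 32, and both documents describe the resulting power as low and a limitation.

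The hypothesis under the Exploratory Aim (SAP, Data Analysis) compares the arms: "The intervention group will have a significantly greater reduction in BP and sodium intake", together with a larger gain in hypertension knowledge, relative to control. The Protocol's post-intervention section gives the main focus of Aim 2 as something else: "We operationalize acceptability, the key Aim 2 outcome".

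**The concern.** There are two linked problems. First, the printed inputs are sufficient to compute power for a 1-df Group x Time interaction, and the answer is not 70% under either common definition of f. Second, the only effect size given is for Time. Both arms receive the educational session, so a Time effect pools change in both arms and says nothing about how much more one arm changes than the other. The effect that the test needs is not stated.

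The 70% figure is the plan's only quantified statement of what the group comparison can show, and the recruitment target rests on it. Read as an interaction, f = 0.39 could mean a between-arm difference in change of 1.56 SD or of 0.78 SD. A null result would be read very differently in the two cases.

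**Working it through.** **Inputs (SAP, Sample size).** f = 0.39; k = 2 groups; m = 2 measurements; r = .5; alpha = .05; N = 28 (14 per arm); target power 70%. Software, effect-size convention and sidedness are not stated.

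**Method.** Noncentral F with df1 = (k-1)(m-1) = 1 and df2 = (N-k)(m-1) = 26.

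**Attempt to reproduce 70% at N = 28** (f² = 0.1521)

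| Convention | Noncentrality λ | Power at N = 28 | Smallest balanced N for 70% |
|---|---|---|---|
| (a) f scaled by r: λ = f²·N·m/(1-r) | 0.1521 × 28 × 2 / 0.5 = 17.04 | 97.8% | 14 (76.4%; N = 12 gives 68.3%) |
| (b1) f absorbs r: λ = f²·N | 0.1521 × 28 = 4.26 | 51.1% | 44 (71.5%; N = 42 gives 69.4%) |
| (b2) f absorbs r: λ = f²·(N-2) | 0.1521 × 26 = 3.95 | 48.2% | 46 (71.6%; N = 44 gives 69.5%) |

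Simulation gave 97.9% for (a) and 50.6% for (b1).

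**Other readings at N = 28**

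- Prior-study value f = 0.395: 98.0% under (a); 49.2-52.1% under (b).
- One df removed for the age covariate: changes of about 0.1 point.
- Correlation ignored (r = 0): 80.2%.
- Between-subject effect, which is not the powered test: 63.1%.
- One-sided .05: 99.1% under (a); 61.5-64.2% under (b); 88.4% with r = 0; 75.0% for the between-subject effect.
- Closest result, using normal approximations and f = 0.395: 67.5%, for a post-score ANCOVA.

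None of these comes within 2 points of 70%.

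**What f = 0.39 would mean as an interaction.** At r = .5 the SD of a change score is SD × √(2 × (1 - .5)) = SD, so a difference d in SD of change equals d in SD at one time point.

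- Under (a), d = 4f = 1.56.
- Under (b1), d = 2f = 0.78.

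As a cross-check, a two-sample comparison of change scores has λ = (N/4)d² = 7d². This gives 7 × 1.56² = 17.04 and 7 × 0.78² = 4.26, as in the table.

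**What the design can detect, independent of convention** (two-sample t test on change scores, two-sided .05, d in SD of change)

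| Subjects analysed | d for 70% power | d for 80% power |
|---|---|---|
| 28 | 0.975 | 1.100 |
| 32 | 0.908 | 1.024 |

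For 28 completers, 70% power corresponds to f = 0.975/4 = 0.244 under (a), or 0.49-0.51 under (b). None of these values appears in the documents.

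**Attrition step.** 28/(1 - 0.11) = 31.5, rounded up to 32. This step is consistent; the fault is confined to N = 28.

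**The case against.** The best defence is that f = 0.39 was never the interaction input. If it describes only Time, failing to obtain 70% from it does not show that 70% or N = 28 is wrong. An interaction f of 0.25 scaled by r, taken purely as an assumption, gives 72.1% at N = 28 and 68.7% at N = 26, which would make 28 the smallest balanced sample reaching 70%. This is possible, but the documents contain no such value, and their sentence presents 0.39 as the value used. If the defence is right, the input that matters is missing and the one printed is misleading, so the text needs the same correction.

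A second argument is that the two conventions are not equally supported. Only scaling by r gives the listed correlation any work to do, and on that reading the plan understates its power. This is fair and makes (a) the more natural reading. It does not exclude (b), since no software or convention is named.

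Some variants do approach 70% at N = 32 (69.3% for the between-subject effect, 69.5% for a one-sided (b)), but the plan attaches 70% to 28 subjects before attrition, and these are a different test or an unstated sidedness.

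Finally, the comparison is exploratory, acceptability is the key outcome, and low power is already conceded. These points limit the consequences, and they stand. They do not make the figure correct: under (a) power is not low, and under (b) it is nearer 50% than 70%.

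**Conclusion.** The concern holds. With the stated inputs, power for the Group x Time interaction at N = 28 is 97.8% or 48.2-51.1%, depending on an unnamed convention, and not 70%. The sample for 70% would be 14 or 44-46. Whether the plan understates or overstates its power cannot be settled from the documents, although the listing of r favours understatement. Separately from the arithmetic, no effect size is given for the between-arm difference in change. The figures assume a two-sided alpha of .05, equal arms and r = .5. They describe a two-group, two-time comparison, as in the sample size paragraph, and not the 2x2x2 layout named in the SAP's analysis section. This is a reporting error worth correcting, and it does not threaten the pilot's key outcome.

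**What to change.** Amend the sample size paragraph in both the SAP and the Protocol, keeping N = 32, in one of two ways.

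1. Drop the Time effect of 0.39 as the basis and state what the design can detect. Suggested text: *With 28 completers and two-sided alpha of .05, the Group x Time interaction has about 70% power for a between-arm difference in change of about 1 SD of the change score (at r = .5, equal to 1 SD of the outcome at one time point; f of about 0.24-0.25 when f is scaled by r).* Add a sentence on whether a difference of that size is plausible.
2. State the interaction f and the convention actually used, justify that f as a between-arm difference in change, and recompute power from it.

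Keep the acknowledgement of low power if the restated figure is about 70% or below. The cost is wording in two places, with no additional subjects and no change to analysis or conduct.

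### The pre-post stability correlation pools both arms, and for sodium it appears to rest on one recall day per time point, so a low r cannot be read as instability

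*SAP*

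**What the plan says.** The SAP (Data Analysis, Aim 2) plans two sets of Pearson correlations. One is "to assess relationships between primary and secondary outcome variables at each data collection point". The other is "to assess the stability of each outcome variable pre- and post-intervention". Neither is restricted to an arm or computed by arm. Sodium intake is one of the outcomes, alongside BP and hypertension knowledge.

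Sodium is measured by the "Automated Self-Administered 24-Hour Dietary Assessment Tool (ASA24) focusing on sodium intake" (Protocol, Baseline data collection). Neither document gives the number of recall days. The same section has baseline questionnaires completed on locked study iPads and adds: "The subjects will not use their own devices and the link are not send to subjects". For controls, there is a four-week "follow-up meeting to collect each subject's BP, ASA24, and post-test knowledge on HTN" (Protocol, Aim 2 Control Group). For all subjects, the section on post-intervention data collection says "We will schedule a post-intervention meeting with each subject for data collection (gold standard BP" and does not name ASA24. At most, its later mention of other study variables covers it.

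BP, by contrast, has a stated replicate: the reading "will be taken twice, five minutes apart to be averaged". Nothing comparable is described for sodium, and the SAP has no measurement-error adjustment and no limit on how the correlations may be read.

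**The concern.** Two separate things can make the pre-post r low when the outcome itself is stable.

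The first applies to every outcome. Half the subjects receive the intervention between the two measurements. If it works, their follow-up values move, by a common amount or by amounts that differ between subjects. A correlation pooled over arms counts that movement as lack of stability.

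The second applies to sodium. One 24-hour recall records one day's intake. Without a replicate at the same time point, day-to-day variation cannot be separated from a change in usual intake, and the correlation of sodium with BP is pulled toward zero.

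At stake is what the pilot reports about its own outcomes: it could describe sodium as unstable, or as unrelated to BP, when the data cannot show either.

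**Working it through.** **Inputs from the documents.** 32 enrolled 1:1; 7-11% attrition; N = 28 needed; r = 0.5 between the two measurements and f = 0.39 in the power calculation. Completers: 32 x (1 - 0.11) = 28.5, or about 28, hence 14 per arm. The plan states no figure for sodium variability, recall reliability or an expected sodium correlation, so it has no figure of its own to reproduce on this point.

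**Assumptions.** VR, the ratio of within- to between-person variance of one day's sodium, is taken over 0.5 to 4. Day-to-day errors are independent between time points. True stability of usual intake is shown at 1.0 and 0.8.

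**Step 1: pooling arms.** Take equal arms, equal expected baseline means, unit SD within each arm and within-arm correlation rho. If one arm's follow-up mean shifts by delta SDs, the covariance is unchanged and the follow-up variance becomes 1 + delta²/4. So

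pooled r = rho / √(1 + delta²/4).

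For scale only, take rho = 0.5 and delta = 2f = 0.78 (the plan attaches f to the Time effect, so this is a borrowed size): 0.5 / √(1 + 0.152) = 0.47. A mean shift of that size costs little. Varying response adds to it: if individual responses have variance tau² (in units of the outcome variance) and are independent of baseline, r within the intervention arm is rho / √(1 + tau²). The documents give nothing from which to set tau. A uniform shift leaves the within-arm r unchanged, so computing r by arm removes the first effect but not the second.

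**Step 2: one recall per time point.** Single-day reliability is R = 1/(1 + VR). Expected pre-post r = R x true stability. Expected sodium-BP r = true r x √R if BP is error-free.

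| VR (assumed) | R | pre-post r, true 1.0 | pre-post r, true 0.8 | sodium-BP factor | true sodium-BP r of 0.30 becomes |
|---|---|---|---|---|---|
| 0.5 | 0.67 | 0.67 | 0.53 | 0.82 | 0.24 |
| 1 | 0.50 | 0.50 | 0.40 | 0.71 | 0.21 |
| 2 | 0.33 | 0.33 | 0.27 | 0.58 | 0.17 |
| 3 | 0.25 | 0.25 | 0.20 | 0.50 | 0.15 |
| 4 | 0.20 | 0.20 | 0.16 | 0.45 | 0.13 |

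BP is not error-free either. With an assumed BP reliability of 0.8, the factor is 0.73 at VR 0.5 and 0.40 at VR 4.

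The r = 0.5 in the power calculation would hold for single-recall sodium only if VR is at most 1 (true stability 1.0: 1/0.5 - 1) or at most 0.6 (true stability 0.8: 0.8/0.5 - 1).

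**Step 3: precision of r.** Fisher z interval: atanh(r) ± 1.96/√(n - 3).

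- n = 28, observed r = 0.27: 0.277 ± 0.392, so 95% CI -0.11 to 0.58.
- n = 28, observed r = 0.40: 95% CI 0.03 to 0.67.
- n = 14 (one arm), observed r = 0.35: 0.365 ± 0.591, so 95% CI -0.22 to 0.74.

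An r of 0.27 is what a true stability of 0.8 would give at VR 2. Nothing in the planned data separates that from intake that really changed.

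**The case against.** The strongest reply is that these correlations are descriptive. The SAP lists them with its preliminary analyses, sets no threshold for calling an outcome unstable, ties no decision to them and never says that it targets usual intake. Acceptability is the key Aim 2 outcome, and the group comparison is exploratory. All of this stands, and it limits the weight of the point. It does not remove it, because the SAP itself labels the pre-post r a measure of stability.

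A reader might also infer four stronger things that the documents do not support:

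- **That one recall per visit is a stated fact.** It is a strong inference from the single listing of ASA24 and the iPad arrangement, which is described only at baseline. For the intervention arm, even the follow-up ASA24 is not explicit.
- **That the sodium correlations mainly reflect day-to-day variation.** This needs VR above 1, and the documents give no variance components. At VR 0.5, two thirds of the single-day variance is between persons.
- **That the correlations cannot be read at all.** Independent day-to-day error shrinks a correlation but does not create one, so a clearly non-zero r remains evidence of association.
- **That the randomized sodium comparison is biased.** Day-to-day noise costs it precision, but does not by itself shift the difference between arms.

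Nor is the control arm free of intervention. All subjects attend the educational session, which covers specific ways to lower BP, so controls may also change over the four weeks.

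**Conclusion.** The point holds in a limited form. The pooled pre-post r mixes response to MOBILE with stability for every outcome. This follows from the wording and needs no variance assumption, although its size is unknown: a mean shift alone may cost little, and varying response could cost more.

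For sodium, if there is one recall per time point as the text implies, the pre-post r is also multiplied by R (0.67 to 0.20) and the sodium-BP r by at most √R (0.82 to 0.45). These ranges rest on the assumed VR of 0.5 to 4 and on independent daily errors. What is barred is one inference: from a low r to unstable usual intake or to no association with BP. It is a matter of analysis wording and interpretation, and it does not undermine the trial's main comparison.

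**What to change.** In the SAP, Data Analysis, Aim 2:

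1. Compute the pre-post r within each arm and report it with a 95% CI. Use the control arm as the cleaner indicator of stability, and note that controls also received the educational session.
2. Report the sodium pre-post r as single-day agreement. State that a low value supports no conclusion about the stability of usual intake, and that a low sodium-BP r does not show absence of association.
3. State the number of ASA24 recalls per time point, and whether the follow-up ASA24 applies to both arms.

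This changes wording only. It needs no added recall day and no change to visits or to intervention delivery. The cost is precision: with about 14 completers per arm, an observed r of 0.35 has a 95% CI of about -0.22 to 0.74, so the by-arm values will be rough and should be presented as such.
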